#### **6.4. Changes from Protocol-Specified Efficacy Analyses**

Due to differences in the treatment regimens in Part A (subcutaneous injection) and Part B (oral administration), the TAF (Part B) oral dose groups will not be compared to the placebo injection group in Part A with respect to the efficacy endpoints.

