The proposed dose range allows for sufficient dose-separation between cohorts for examining safety, antiviral activity and pharmacokinetics of a single dose of oral TAF, and maximizes the probability of observing a dose/exposure -response relationship. Since there are sufficient subjects in the placebo group from Part A, and the safety of TAF >125 mg is unknown, all subjects in Part B will be enrolled to receive TAF.

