3.2. Study Design

Randomized, double-blinded, placebo-controlled, multi-cohort study of GS-6207 (Part A) and single-arm study of TAF (Part B) monotherapy in subjects with HIV-1 infection

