8.5. Efficacy Analysis

8.5.1. Primary Analysis

Data from the placebo recipients in all cohorts will be combined to form one placebo group for the purpose of analysis. Each of the GS-6207 and TAF treatment group will be compared to the pooled placebo group with respect to the primary efficacy endpoint, the maximum reduction of plasma HIV-1 RNA (\log_{10} copies/mL) from Day 1 through Day 10, using the 2-sided t-test conducted at an alpha level of 0.05.

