**Part B:**

A single dose of TAF will be administered orally in the morning under fasted conditions on Day 1. The doses to be evaluated in Cohorts 7-8 will be determined based on cumulative safety (through at least Day 14), available PK, and viral kinetic data from previous cohorts. Selected doses will be either lower than, or no more than 3-fold higher than, previously evaluated doses in this study. Cohorts 7 and 8 may be run in parallel.

The protocol prespecified dose and actual dose used for each cohort are provided below. Cohort 8 was not initiated due to observed antiretroviral activity from Cohorts 6 and 7 which did not demonstrate durable activity over 10 days.

Cohort	Protocol Prespecified Dose of TAF	Actual Dose of TAF
6	200 mg	200 mg 
7	Up to 600 mg	600 mg 
8	Up to 600 mg	Did not enroll

 Subjects enrolled in Cohort 6 (200 mg) and Cohort 7 (600 mg) will be given 8 and 24 tablets of TAF 25 mg tablet, respectively.

All subjects in Part A and Part B will initiate once-daily bictegravir/emtricitabine/tenofovir alafenamide (B/F/TAF, 50/200/25 mg) on Day 10 and be treated to Day 225.

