#### **Part B**

A sample size of 8 subjects in each TAF treatment group and a total of 10 subjects in the placebo group will provide 99% power to detect a treatment difference of 1.43  $\log_{10}$  copies/mL in maximum reduction of HIV-1 RNA between at least one of the TAF treatment groups and the placebo group from Part A of the study. In this power analysis, it is assumed that a common SD for maximum reduction in HIV-1 RNA is 0.52  $\log_{10}$  copies/mL (based on Studies GS-US-120-0104 and GS-US-120-1101) and a 2-sided t-test is conducted at an alpha level of 0.05.

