#### **6.3.2. Analysis of Other Efficacy Endpoints**

Baseline values, values at each visit, and the change from baseline in HIV-1 RNA ( $\log_{10}$  copies/mL) by visit will be summarized by treatment group. Pairwise comparison of the change from baseline in HIV-1 RNA ( $\log_{10}$  copies/mL) among all treatment groups and placebo at each visit through Day 10 will be performed in the same manner as that of the primary efficacy endpoint.

Mean  $\pm$  95% confidence interval (CI) and median (Q1, Q3) of the change from baseline in HIV-1 RNA ( $\log_{10}$  copies/mL) will be plotted to Day 10 using a line plot by treatment group and visit.

Number and percentage of subjects with HIV-1 RNA < 50 copies/mL by visit will be analyzed using the missing excluded method, where missing data will be excluded in the computation of the percentages (ie, missing data points will be excluded from both numerator and denominator in the computation). The denominator for percentages at a visit is the number of subjects in the FAS with nonmissing HIV-1 RNA value at that visit. No statistical testing is planned. The number and percentage of subjects with HIV-1 RNA in the following categories will be summarized:

- < 50 copies/mL
  - < 20 copies/mL
    - < 20 copies/mL Not Detectable
    - < 20 copies/mL Detectable
  - 20 to < 50 copies/mL
- 50 to < 200 copies/mL
- 200 to < 400 copies/mL
- 400 to < 1000 copies/mL
- $\geq$  1000 copies/mL

Baseline values, values at each visit, and the change from baseline in CD4 cell count ( $\mu$ L) by visit will be summarized by treatment group. No statistical testing is planned.

All efficacy endpoints will be conducted using the FAS.

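### SAP 6.4 withdraws the Part B comparison with placebo, but SAP 1.3 still states 99% power for it and SAP 6.1 does not say how the Part B primary endpoint will be analysed

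*SAP*

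**What the plan says.** **Protocol.** Section 3.2 describes Part B as a "single-arm study of TAF (Part B) monotherapy in subjects with HIV-1 infection". Section 8.5.1 nevertheless gives it a comparative primary analysis by 2-sided t-test at 0.05: "Each of the GS-6207 and TAF treatment group will be compared to the pooled placebo group with respect to the primary efficacy endpoint". Section 8.8 sizes Part B on that test. Section 1.5.2 gives two reasons for having no placebo arm in Part B. One is reliance on Part A ("Since there are sufficient subjects in the placebo group from Part A"); the other is that the safety of TAF above 125 mg is unknown.

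**SAP.** Section 6.4 states that "the TAF (Part B) oral dose groups will not be compared to the placebo injection group in Part A", citing injection in one part and oral dosing in the other. Section 6.1 then describes tests of the lenacapavir groups against pooled placebo and against each other, and does not mention TAF. Two other places were not adjusted:

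- Section 1.3, Part B, still claims 99% power to detect 1.43 log10 "between at least one of the TAF treatment groups and the placebo group from Part A of the study".
- Section 6.3.2 still asks for pairwise tests of change from baseline "among all treatment groups and placebo at each visit through Day 10 will be performed", without naming a part.

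Section 1.2 of the same SAP reports that "Cohort 8 was not initiated due to observed antiretroviral activity from Cohorts 6 and 7", and section 2.1 describes the interim analyses as already conducted.

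**The concern.** A reader who takes SAP 1.3 at face value will believe that Part B delivers a highly powered controlled test of TAF. Under SAP 6.4 it delivers no controlled test. A reader who goes to SAP 6.1 for the analysis of the Part B primary endpoint finds none named: no statistic, interval, reference value or contrast between the two TAF doses.

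The choice of endpoint makes this more than an editorial matter. The largest drop among several noisy measurements tends to be positive whether or not the drug works, and a control group absorbs that bias. Without a control, a positive TAF mean or an interval excluding zero could be taken as evidence of activity when part of it is an artefact of taking a maximum.

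**Working it through.** **1. The stated power.** Inputs from SAP 1.3, Part B: 8 TAF and 10 placebo subjects, difference 1.43, SD 0.52, 2-sided alpha 0.05.

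- Standard error = 0.52 × √(1/8 + 1/10) = 0.52 × 0.4743 = 0.2467.
- Noncentrality = 1.43 / 0.2467 = 5.80, with 16 degrees of freedom.
- Power = 0.9997 (noncentral t), or 0.9999 by normal approximation. The difference detectable with 99% power is 1.13 log10.

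The stated 99% is met. The figure is not miscalculated; it belongs to a test that SAP 6.4 removes.

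**2. What the final plan delivers per TAF dose.** Same n and SD, one group:

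- Half-width of the 95% confidence interval = t(0.975; 7) × 0.52/√8 = 2.365 × 0.1838 = 0.43 log10.

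**3. The endpoint with no drug effect.** Scheduled post-dose samples through Day 10 fall on Days 2, 3, 4, 7, 8, 9 and 10 (7 values). Part B adds Days 5 and 6 where possible (up to 9). The footnote to SAP Table 3-1 says that all HIV-1 RNA data enter the maximum, regardless of visit windows.

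- *Share with a positive value.* If baseline and the k later values are exchangeable, the maximum reduction is positive unless baseline is the smallest of the k + 1 values. The probability is k/(k + 1): 7/8 for k = 7 and 9/10 for k = 9. This needs no variance figure.
- *Expected size.* With independent normal errors of SD s, the mean is s times the expected maximum of k standard normal values, which is 1.35 for k = 7 and 1.485 for k = 9. The documents give no within-subject SD, so a range is assumed:

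| Assumed SD (log10) | 7 values | 9 values |
|---|---|---|
| 0.15 | 0.20 | 0.22 |
| 0.20 | 0.27 | 0.30 |
| 0.30 | 0.41 | 0.45 |

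Simulation agrees to within 0.01. Against the 1.43 planning effect this is 0.20/1.43 = 14% to 0.45/1.43 = 31%. The two additional Part B days raise the expected value by (1.485 − 1.35) × s, or about 0.02 to 0.04 log10.

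**4. What the SAP supplies by default.** SAP 3 provides general descriptive statistics, with Parts A and B summarised separately, and SAP 3.2 groups subjects by dose. So each TAF dose gets a mean, SD or SE, median, quartiles and range. No confidence interval for the primary endpoint is specified for Part B; the 95% intervals in SAP 6.3.2 belong to the plot of change from baseline by visit.

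**The case against.** The strongest reply is that nothing essential is lost. The Part A objective is worded against placebo; the Part B objective (Protocol 2, SAP 1.1) is only to evaluate the antiviral activity of TAF. A descriptive result meets it, and the general rules in SAP 3 and 3.2 supply one. This stands, so it would be too strong to infer that the Part B objective is left without any analysis. What was withdrawn is the protocol's primary analysis, and SAP 6.1 should say what takes its place.

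Readers also have some context: the pooled placebo result in Part A, and mean Day 10 reductions of 0.99 to 1.52 log10 with daily TAF in Protocol 1.5.2. That is fair, but those figures describe Day 10 change rather than the maximum, and the SAP names neither source as a benchmark. The plot of change by visit in SAP 6.3.2 is free of the maximum bias.

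Section 6.3.2 says its tests follow the manner of the primary analysis, and 6.4 excludes TAF versus placebo for the efficacy endpoints. Read together, the three sections can be reconciled. The wording is loose and needs a limit, but it is not a firm contradiction.

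A reader might infer that the comparison was dropped because of the Part B results. The documents do not support that. They show that the SAP recording the change also reports Cohort 6 and 7 activity, and that the route difference given as the reason was already in the protocol. They give no date for the decision, and the revision table in SAP 11 is blank. Interim reviews of Part B were planned (Protocol 8.9), the change is disclosed in the proper section, and it gives up a test with very high planned power. No motive should be alleged.

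Nor was the Part A placebo group the only reason for a single-arm Part B; Protocol 1.5.2 also cites unknown safety above 125 mg.

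**Conclusion.** The point holds as a failure to reconcile the SAP with its own section 6.4. The 99% power in SAP 1.3 is a property that the final plan does not have, and the analysis of the Part B primary endpoint is left to general conventions. The replacement figure is a half-width of about 0.43 log10 per TAF dose, which rests on n = 8 per cohort and the SAP's SD of 0.52.

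The caution against reading the mean against zero is firm in direction: 7/8 to 9/10 of subjects would show a positive value under exchangeability alone. Its size, about 0.2 to 0.45 log10, depends on an assumed within-subject SD of 0.15 to 0.30 and independent normal errors.

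Dropping the comparison is defensible in itself, since it was non-randomised and crossed routes of administration. The documents do not show that the decision was driven by data.

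**What to change.** 1. **SAP 1.3, Part B:** mark the power statement as superseded by 6.4. Replace it with precision: n = 8 per dose, SD 0.52, 95% confidence half-width about 0.43 log10.
2. **SAP 6.1:** state that the Part B primary endpoint is analysed descriptively by TAF dose, with mean and 95% confidence interval. Add that the value is expected to exceed zero without a drug effect and is not to be read against zero.
3. **SAP 6.3.2:** limit the comparisons with placebo to Part A, and say whether the two TAF doses are to be compared with each other.
4. **SAP 6.4:** record when the change was decided and which Part B data were known at the time.

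Optionally, add a supportive difference between each TAF dose and pooled placebo with its 95% confidence interval, labelled non-randomised, with the maximum taken over the days common to both parts (2, 3, 4, 7, 8, 9 and 10). This restores a reference for the bias of the maximum, but compares open-label oral dosing with blinded injection.

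Items 1 to 4 cost a few sentences and the loss of a favourable-looking power figure. The optional analysis costs one table and a caveat. No new data are needed.

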## **7. SAFETY ANALYSES**

### **7.1. Adverse Events and Deaths**

#### **7.1.1. Adverse Event Dictionary**

Clinical and laboratory AEs will be coded using the current version of MedDRA. System organ class (SOC), high-level group term (HLGT), high-level term (HLT), preferred term (PT), and lower-level term (LLT) will be provided in the AE dataset.

#### **7.1.2. Adverse Event Severity**

Adverse events are graded by the investigator as Grade 1, 2, 3, or 4 according to toxicity criteria specified in the protocol. The severity grade of events for which the investigator did not record severity will be categorized as “missing” for tabular summaries and data listings. The missing category will be listed last in summary presentation.

#### **7.1.3. Relationship of Adverse Events to Study Drug**

Related AEs are those for which the investigator selected “Related” on the AE CRF to the question of “Related to Study Treatment.” Relatedness will always default to the investigator’s choice, not that of the medical monitor. Events for which the investigator did not record relationship to study drug will be considered related to study drug for summary purposes. However, by-subject data listings will show the relationship as missing.

#### **7.1.4. Serious Adverse Events**

Serious adverse events (SAEs) will be identified and captured as SAEs if the AEs met the definitions of SAEs that were specified in the study protocol. SAEs captured and stored in the clinical database will be reconciled with the SAE database from the Gilead Global Patient Safety (GLPS) Department before data finalization.

#### **7.1.5. Treatment-Emergent Adverse Events**

##### **7.1.5.1. Definition of Treatment-Emergent Adverse Events**

Treatment-emergent adverse events (TEAEs) are defined as any AE with an onset date on or after the study drug start date.

##### **7.1.5.2. Incomplete Dates**

If the onset date of the AE is incomplete and the AE stop date is not prior to the first dose date of study drug, then the month and year (or year alone if month is not recorded) of onset determine whether an AE is treatment emergent. The event is considered treatment emergent if the AE onset is the same as or after the month and year (or year) of the first dose date of study drug.

An AE with completely missing onset and stop dates, or with the onset date missing and a stop date later than the first dose date of study drug, will be considered to be treatment emergent (and included in both TEAE summaries up to Day 10 and throughout the study.) In addition, an AE with the onset date missing and incomplete stop date with the same or later month and year (or year alone if month is not recorded) as the first dose date of study drug will be considered treatment emergent (and included in both TEAE summaries up to Day 10 and throughout the study).

#### **7.1.6. Summaries of Adverse Events and Deaths**

Treatment-emergent AEs will be summarized based on the Safety Analysis Set.

##### **7.1.6.1. Summaries of AE Incidence in Combined Severity Grade Subsets**

A brief, high-level summary of the number and percentage of subjects who experienced at least 1 TEAE in the categories described below will be provided by treatment group for TEAEs with onset date reported up to Day 10 (prior to the B/F/TAF first dose date) and throughout the study, respectively. All deaths observed in the study will also be included in this summary.

The number and percentage of subjects who experienced at least 1 TEAE will be provided and summarized by SOC, HLT (if applicable), PT, and treatment group.

- TEAEs

For the AE categories described below, summaries will be provided by SOC, PT, and treatment group:

- TEAEs with Grade 3 or higher (by severity)
- TE treatment-related AEs
- TE treatment-related AEs with Grade 3 or higher (by severity)
- TEAEs leading to death (ie, outcome of death)
- TE SAEs
- TE treatment-related SAEs
- TEAEs leading to premature discontinuation of study drug
- TEAEs leading to premature discontinuation of study

Multiple events will be counted only once per subject in each summary. Adverse events will be summarized and listed first in alphabetic order of SOC (and HLT within each SOC if applicable), and then by PT in descending order of total frequency within each SOC. For summaries by severity grade, the most severe grade will be used for those AEs that occurred more than once in an individual subject during the study.

In addition to the above summary tables, for the AE categories described below, summaries will be provided by PT only in descending order of total frequency:

- TEAEs
- TE SAEs

In addition, data listings will be provided for the following:

- All AEs
- All SAEs
- All Deaths
- All AEs leading to death (ie, outcome of death)
- All AEs with severity of Grade 3 or higher
- All AEs leading to premature discontinuation of study drug
- All AEs leading to premature discontinuation of study
- All AEs for COVID-19 and Suspected COVID-19 infection, defined as AE preferred terms of “Suspected COVID-19”, “COVID-19”, “COVID-19 pneumonia”, or “Asymptomatic COVID-19”

For each listing, whether the event is treatment emergent will be indicated.

## **7.2. Laboratory Evaluations**

Laboratory data collected during the study will be analyzed and summarized using both quantitative and qualitative methods. Summaries of laboratory data will be provided for the Safety Analysis Set and will include data collected throughout the study. The analysis will be based on values reported in conventional units. When values are below the LOQ, they will be listed as such, and the closest imputed value will be used for the purpose of calculating summary statistics as specified in Section 3.7.

A by-subject listing for laboratory test results will be provided by subject ID number and visit in chronological order for hematology, serum chemistry, and urinalysis separately. Values falling outside of the relevant reference range and/or having a severity grade of 1 or higher on the Gilead Grading Scale for Severity of Adverse Events and Laboratory Abnormalities will be flagged in the data listings, as appropriate.

No formal statistical testing is planned.

### **7.2.1. Summaries of Numeric Laboratory Results**

Descriptive statistics will be provided by treatment group for each laboratory test specified in the study protocol as follows:

- Baseline values
- Values at each postbaseline visit
- Change from baseline at each postbaseline visit

A baseline laboratory value will be defined as the last measurement obtained on or prior to the date/time of first dose of study drug. Change from baseline to a postbaseline visit will be defined as the visit value minus the baseline value. The mean, median, Q1, Q3, minimum, and maximum values will be displayed to the reported number of digits; SD values will be displayed to the reported number of digits plus 1.

In the case of multiple values in an analysis window, data will be selected for analysis as described in Section 3.8.3.

### **7.2.2. Graded Laboratory Values**

The Gilead Grading Scale for Severity of Adverse Events and Laboratory Abnormalities will be used to assign toxicity grades (0 to 4) to laboratory results for analysis. Grade 0 includes all values that do not meet the criteria for an abnormality of at least Grade 1. For laboratory tests with criteria for both increased and decreased levels, analyses for each direction (ie, increased, decreased) will be presented separately.

#### **7.2.2.1. Treatment-Emergent Laboratory Abnormalities**

Treatment-emergent laboratory abnormalities are defined as values that increase at least 1 toxicity grade from baseline at any postbaseline visit. If the relevant baseline laboratory value is missing, any abnormality of at least Grade 1 observed within the time frame specified above will be considered treatment emergent.

#### **7.2.2.2. Summaries of Laboratory Abnormalities**

Laboratory data that are categorical will be summarized using the number and percentage of subjects in the study with the given response at baseline and each scheduled postbaseline visit.

The following summaries (number and percentage of subjects) for treatment-emergent laboratory abnormalities will be provided by lab test and treatment group; subjects will be categorized according to the most severe postbaseline abnormality grade for a given lab test:

- Graded laboratory abnormalities (note: in addition to summarizing abnormalities throughout the study, a separate table will summarize abnormalities reported up to Day 10, collected on or prior to the B/F/TAF first dose date)
- Grade 3 or 4 laboratory abnormalities

For all summaries of laboratory abnormalities, the denominator is the number of subjects with nonmissing postbaseline values.

A by-subject listing of treatment-emergent laboratory abnormalities and treatment-emergent Grade 3 or 4 laboratory abnormalities, respectively, will be provided by subject ID number and visit in chronological order. This listing will include all test results that were collected throughout the study for the lab test of interest, with all applicable severity grades and abnormal flags displayed.

